# 8. STUDY POPULATION

## 8.1. Subject Inclusion Criteria (Part 1 and Part 2)

A subject must meet all the following criteria for enrollment:

- 1. At least 18 years of age at time of informed consent.
- 2. Diagnosis of active SARS-CoV-2 infection. Presence of SARS-CoV-2 viral RNA or viral antigen may be detected in respiratory specimens (collected using nasopharyngeal or oropharyngeal swabs) with a qualitative nucleic acid amplification test (such as RT-PCR) or viral antigen test or other diagnostic method that is authorized, cleared, or approved by the US Food and Drug Administration (or equivalent local authority) for SARS-CoV-2 viral detection. Note: Serology-based antibody tests do not detect presence of virus, and therefore are not considered diagnostic for active infection and cannot be used for study eligibility screening or for subsequent SARS-CoV-2 assessments.
- 3. Have respiratory failure requiring oxygen supplementation or have either invasive or noninvasive mechanical ventilation with PaO2/FiO2 ratio >100 mm Hg. Respiratory failure cannot be fully explained by cardiac failure or fluid overload.
  - a. The ABG test result is used to determine the PaO2/FiO2 ratio. An ABG test should be performed for every subject, but if an ABG result cannot be obtained, the peripheral oxygen saturation (SpO2) can be measured and the SpO2/FiO2 ratio can be used.
  - b. If the SpO2/FiO2 ratio is used for inclusion in the study, it must be >89. See Appendix 1 for more details.
- 4. Written informed consent for study participation must be provided by the subject (or legally authorized representative) prior to any study-related procedures.
- 5. Subject (or legally authorized representative) is willing and able to comply with study procedures and assessments, including imaging assessments and venous blood sample(s) per protocol.
- 6. Each female subject of childbearing potential must have a negative serum pregnancy test at screening and must agree to use protocol-defined methods of contraception from screening through at least 90 days after receiving the last dose of APL-9.
- 7. Male subjects must agree to use protocol-defined methods of contraception and agree to refrain from donating semen from screening through at least 90 days after receiving the last dose of APL-9.

Acceptable methods of contraception are described in Section 11.2.8. Contraceptive use by men or women should be consistent with local regulations regarding the methods of contraception for those participating in clinical studies.

# 8.2. Subject Exclusion Criteria (Part 1 and Part 2)

Subjects are excluded from the study if any of the following criteria apply:

1. Female subjects being pregnant or breastfeeding

- 2. Active bacterial, fungal, or parasitic infection
- 3. History of neuromuscular degenerative disease (eg, amyotrophic lateral sclerosis, Duchenne muscular dystrophy, or multiple sclerosis)
- 4. Current participation in a clinical study with an investigational drug or biologic. NOTE: Participation in studies with the following therapies is NOT excluded:
  - a. Therapies approved (indicated) for COVID-19 by the applicable health authority
  - b. Therapies with emergency use authorization for COVID-19 by the US Food and Drug Administration or equivalent authorization by the applicable health authority
  - c. Therapies approved (indicated) by the applicable health authority and used for COVID-19 as part of standard care
- 5. Treatment with immune checkpoint inhibitors or other immunomodulators within 3 months prior to study enrollment (however, treatment with convalescent plasma, steroids, IL-6 inhibitors, and antiviral agents is NOT excluded)
- 6. Subjects who have, at screening, been on mechanical ventilation for >7 days
- Evidence of kidney failure AND liver failure at screening (estimated glomerular filtration rate <45 mL/min/1.73 m^2 and alanine aminotransferase level >5× the upper limit of normal, as assessed by the local laboratory)
- 8. Subjects with a hereditary complement deficiency

## 8.3. Lifestyle Considerations

Because of the nature of the study, no lifestyle considerations are applicable.

## 8.4. Screening Failures

Sites may initiate screening procedures prior to a subject's diagnosis of respiratory failure or ARDS. Confirmation of SARS-CoV-2 infection may be completed more than 7 days before baseline. All other inclusion and exclusion criteria must be met within –7 days of baseline. Screening failure is defined as the situation of a subject who consents to participate in the clinical study but does not receive study treatment. A minimal set of screening failure information is required to ensure transparent reporting of screening failures to meet the Consolidated Standards of Reporting Trials publishing requirements and to respond to queries from regulatory authorities. Minimal information includes demography, screening failure details, eligibility criteria, and any SAEs.

Subjects may be rescreened with approval from the sponsor.

## 9. TREATMENT OF SUBJECTS

## 9.1. Study Interventions

All subjects participating in this study independent of randomization shall receive the institutional SOC at the discretion of the investigator, to treat their conditions including (but not limited to) supplemental oxygen, mechanical ventilation, fluid management, and required medication as provided by the hospital and allowed by the protocol.

APL-9 is supplied in 6-mL glass vials. Changes to sponsor-supplied packaging prior to dosing may not occur without full agreement, in advance, by Apellis Pharmaceuticals, Inc.

Labels containing study information and pack identification are applied to the investigational product containers.

All investigational product is labeled with a minimum of the following: protocol number, dosage form (including product name and quantity in pack), route of administration, directions for use, storage conditions, batch number and/or packaging reference, the statements "For clinical trial use only" and/or "CAUTION: New Drug—Limited by Federal (or US) Law to Investigational Use," and name and address of the sponsor.

Additional labels may, on a case-by-case basis, be applied to the investigational product in order to satisfy national, local, or institutional requirements but must not do any of the following: contradict the clinical study label, obscure the clinical study label, or identify the study subject by name.

Additional labels may not be added without the prior full agreement of Apellis Pharmaceuticals, Inc.

#### 9.1.1. Study Drug Administration

APL-9 is provided in sterile vials, each containing 180 mg of APL-9 in 6 mL buffer (30 mg/mL). Study drug infusion bags are prepared by an unblinded pharmacist at the study site by dilution of the study drug in isotonic saline for infusion and transferred to site personnel for administration to subjects according to their assigned randomization numbers. Two types of infusion bags containing APL-9 will be prepared:

- 50-mL bag containing 1 vial of APL-9 (ie, 180 mg of APL-9 in 50 mL)
- 250-mL bag containing 1 vial of APL-9 (ie, 180 mg of APL-9 in 250 mL)

Dosing of subjects receiving APL-9 either as open-label treatment or by random, blinded assignment must occur on Day 1, on the same day as randomization, and will be initiated with an IV infusion of 180 mg APL-9 in 50 mL of saline over a 10-minute period, followed within 1 hour by continuous infusion of 180 mg APL-9 in 250 mL saline at the rate of 15 mg/h (approximately 21 mL/h) until the end of study drug administration as follows:

• Part 1: at Day 7 or until or resolution of ARDS (PaO2/FiO2 ratio >300 mm Hg), whichever occurs earlier

• Part 2: at Day 7 or up to and including the approved treatment duration, discontinuation of respiratory support (supplemental oxygen or mechanical ventilation), or hospital discharge, whichever occurs latest

This results in the infusion of two 250-mL bags, each containing 180 mg of APL-9, every 24 hours.

Dosing of subjects randomly assigned to vehicle control must occur on Day 1, on the same day as randomization, and will be initiated with an IV infusion of 50 mL of saline over a 10-minute period followed immediately (and up to and including within 1 hour) by continuous infusion of approximately 21 mL of saline per hour until the end of study drug administration at Day 7 (or approved treatment extension), discontinuation of respiratory support (oxygen supplementation or mechanical ventilation), or hospital discharge, whichever occurs latest. This results in the infusion of 2 bags of 250 mL saline every 24 hours.

Research nurses or other appropriately qualified personnel will administer the IV infusions.

The pharmacists and investigator can change the size of the infusion bags in the event that 50-mL and 250-mL isotonic saline bags are in short supply if:

- the infusion rates of a 180-mg loading dose of APL-9 in the initial 10 minutes and 15 mg/h thereafter to subjects receiving APL-9 are maintained and
- vehicle-only bags of identical size and appearance are given to the vehicle control group.

In the event that isotonic saline for infusion is not available, the pharmacists must contact Apellis Pharmaceuticals, Inc, to select an alternative vehicle.

The treatments are intended to continue to either Day 7 or until the subject no longer requires respiratory support (oxygen supplementation or mechanical ventilation) or is discharged from the hospital (whichever occurs later), except upon allowance by the DMC and by investigator discretion to administer treatment up to and including Day 21 (Part 2 only; extended treatment will be allowed only in subjects who still require respiratory support at Day 7 with an improved PaO2/FiO2 ratio of at least 20 mm Hg from baseline if ABG test results are available for comparison. If ABG test results are not available, an improvement in FiO2 of at least 4% in nonventilated patients (eg, those on nasal cannula) and 10% in mechanically ventilated patients is needed. FiO2 should be weaned following the site's protocol to keep oxygen saturation at 89% or above. Treatment beyond Day 7 and up to and including any DMC-approved extension will be at the discretion of the investigator. If treatment is interrupted for any reason for more than 24 hours, treatment may not be resumed.

A relapse of respiratory failure or ARDS due to COVID-19 must be reported as an AE. Under no circumstances can study drug be administered beyond the DMC-approved treatment window, and treatment may not be reinitiated if it is discontinued.

The SOC to be used at each study site will be determined by the investigator. A recent guideline for the treatment of critically ill patients with COVID-19 has been published and should be considered (CDC 2020).

Infusion-related reactions that occur during the administration of the 50- mL loading dose should be treated as follows:

- For mild infusion-related reactions: The 50 mL bag infusion time should be increased from 10 min to 20-40 min and the reaction should be monitored. Treatment with diphenhydramine may be required. The infusion time of the 250-mL bag should not be increased.
- For severe or persistent mild infusion-related reactions (instances in which the subject's symptoms do not respond to the increased infusion time): treatment should be discontinued, and the institution's emergency hypersensitivity protocol should be employed.

#### 9.1.2. Empiric Antibiotic Treatment for Possible Infection

Body temperature, vital signs, relevant blood parameters, and bacterial cultures will be monitored regularly throughout the study to assess for signs of secondary bacterial infections. All enrolled subjects will receive a broad-spectrum antibiotic during the treatment period to cover possible additional serious bacterial infections (see Section 9.5 for details). Subjects who are discharged prior to the allowable treatment duration will have follow-up conducted by phone and will be provided with emergency study cards that include a list of symptoms associated with infections. The study card also guides subjects with instructions to contact their study physician or seek emergency medical care in the event they experience any of the listed symptoms.

## 9.2. Preparation, Handling, Storage, and Accountability

- 1. The investigational product should be stored frozen at a nominal temperature of -20 °C. Temperature monitoring is required at the investigator site (or documented storage location) to ensure that the investigational product is maintained within a defined and maintained temperature range.
- 2. The investigator or designee must confirm appropriate temperature conditions have been maintained during transit for all study drug received and any discrepancies are reported and resolved before use of the study intervention.
- 3. Only subjects enrolled in the study and assigned to active treatment may receive study drug and only authorized site staff may supply or administer study drug. All study drug must be stored in a secure, environmentally controlled, and monitored area in accordance with the labeled storage conditions with access limited to the investigator and authorized site staff.
- 4. The investigator, institution, or the head of the medical institution (where applicable) is responsible for study drug accountability, reconciliation, and record maintenance (ie, receipt, reconciliation, and final disposition records). Where allowed, the investigator may choose to delegate drug accountability responsibilities to a pharmacist or other appropriate individual.
- 5. Apellis Pharmaceuticals, Inc, or the clinical study sites may supply infusion sets and saline bags as required. Refer to the pharmacy manual for further details.

- 6. All unused and used study drug vials should be retained at the study site until they are inventoried by the study monitor. All used, unused, or expired study drug vials will be returned to Apellis Pharmaceuticals, Inc, or its designee for destruction, and destruction will be documented, or if authorized, disposed of at the study site per the site's standard operating procedures and documented. Please refer to the pharmacy manual for further guidance and information.
- 7. Please refer to the pharmacy manual for further guidance and information.

## 9.3. Measures to Minimize Bias: Randomization and Blinding

#### 9.3.1. Randomization

The first 6 subjects enrolled will be assigned to open-label APL-9 treatment. For the remaining 60 subjects, approximately 30 subjects will be enrolled in each treatment arm for a total of approximately 60 subjects. Subjects will be randomly assigned (1:1) to receive either APL-9 in addition to SOC or vehicle control plus SOC. Randomization will be stratified by need of mechanical ventilation (yes vs no) and age (younger than 65 years vs at least 65 years).

#### 9.3.2. Blinding (Part 2 Only)

All subjects or their legally assigned representatives, investigators, and all study personnel involved in the conduct of the study, including data management and biostatistics, will be blinded to treatment assignment. Study drug infusion bags are prepared by dilution of the study drug in isotonic saline for infusion by an unblinded pharmacist at the study site and transferred to site personnel for administration to subjects according to their assigned randomization number.

Unblinded tables, figures, and listings will be provided to the DMC for review. An unblinded, independent biostatistician will be assigned to prepare the randomization schedule and unblinded tables, figures, and listings for the DMC. The unblinded statistician will not otherwise participate in study procedures.

Unblinding is discouraged but will be permitted in a medical emergency that requires immediate knowledge of the subject's assigned treatment. All subjects should be treated as though they are receiving APL-9. Emergency unblinding will be acceptable only if it affects the medical management of the subject.

## 9.4. Treatment Compliance

Subjects will receive study drug directly from the investigator or designee, under medical supervision. The date, time, and duration of each dose administered will be recorded in the source documents and in the electronic case report form (eCRF). If treatment is interrupted for any reason for greater than 24 hours, treatment may not be resumed.

## 9.5. Concomitant Medications

Any medications administered (including over-the-counter or prescription medicines, vitamins, and/or herbal supplements), and all procedures performed within 4 weeks of screening will be recorded as prior medications and procedures. Oral history is acceptable from the subject or

caregiver. Medications administered and procedures performed from the time of informed consent through the end-of-treatment visit must be recorded as concomitant, along with:

- Reason for use
- Dates of administration including start and end dates
- Dosage information including dose and frequency

All enrolled subjects will receive a broad-spectrum antibiotic during the treatment period to provide coverage for *Neisseria meningitidis*, *Streptococcus pneumoniae*, and *Haemophilus influenzae* unless contraindicated because of hypersensitivity or allergy. Treatment with antibiotics may be adjusted according to culture results and at the discretion of the investigator.

The medical monitor should be contacted if there are any questions regarding concomitant or prior therapy.

#### 9.5.1. Restricted and Prohibited Medications

The use of any approved or investigational anticomplement therapy other than APL-9 is prohibited within 5 half-lives of that product prior to screening. Use of corticosteroids is permitted. Treatment with immune checkpoint inhibitors or other immunomodulators is prohibited during the study (however, treatment with steroids, IL-6 inhibitors, and antiviral agents is NOT excluded).

#### 9.6. Intervention After the End of the Study

There is no intervention following the end of the study. Any additional care provided to subjects after they complete or discontinue the study will be provided by the subjects' personal physicians according to what is normally expected for their conditions.

## 10. DISCONTINUATION OF STUDY INTERVENTION AND SUBJECT DISCONTINUATION/WITHDRAWAL

#### **10.1.** Discontinuation of Study Intervention

Treatment with study drug (APL-9 IV or matching vehicle IV infusion) will terminate as follows:

- Part 1: at Day 7 or until or resolution of ARDS (PaO2/FiO2 ratio >300 mm Hg), whichever occurs earlier
- Part 2: at Day 7 or up to and including the approved treatment duration, discontinuation of respiratory support (supplemental oxygen or mechanical ventilation), or hospital discharge, whichever occurs latest

In Part 2, the DMC may decide to allow treatment with study drug beyond Day 7. If allowed by the DMC, study drug infusions can be extended at the discretion of the investigator beyond Day 7 up to and including Day 21. In Part 2, dosing may be extended only in subjects who still require respiratory support (oxygen supplementation or mechanical ventilation) at Day 7 with a PaO2/FiO2 ratio improved by at least 20 mm Hg from baseline if ABG test results are available for comparison. If ABG test results are not available, an improvement of FiO2 of at least 4% in nonventilated patients (eg, those on nasal cannula) and 10% in mechanically ventilated patients is needed. FiO2 should be weaned following the site's protocol to keep oxygen saturation at 89% or above. Treatment beyond Day 7 and up to and including any DMC-approved extension will be at the discretion of the investigator. However, study drug administration must end at the DMC-allowed maximal time point or upon the subject's discharge from the hospital. The time of transfer and termination of study drug treatment must be recorded in the subject's medical records and eCRF. If treatment is interrupted for any reason for greater than 24 hours, treatment may not be resumed.

In rare instances, it may be necessary for a subject to permanently discontinue study treatment (definitive discontinuation). The date of and reason for treatment discontinuation must be determined by the investigator and recorded in the subject's medical record and on the appropriate eCRF. If it is determined that there was more than one reason for the discontinuation, each reason should be documented in the source document and the most clinically relevant reason, as determined by the investigator, should be entered on the eCRF (see also Section 10.2).

Any subject who discontinues treatment early or is withdrawn from the study early because of a TEAE, whether serious or nonserious, will be followed up until the TEAE resolves (returns to normal or baseline values) or stabilizes or until it is judged by the investigator to no longer be clinically significant.

If study treatment is definitively discontinued, the subject will remain in the study to be evaluated for safety. See the schedule of assessments (SoA) for data to be collected at the time of discontinuation of study treatment, discharge, and safety follow-up and for any further evaluations to be completed.

### **10.2.** Subject Discontinuation/Withdrawal From the Study

- A subject may withdraw from the study at any time at his/her own request (or at the request of his/her legal representative) or at the discretion of the investigator for safety, behavioral, compliance, or administrative reasons.
- At the time of discontinuing from the study, if possible, an end-of-treatment visit should be conducted, as shown in the SoA. See the SoA for data to be collected at the time of study discontinuation and follow-up and for any further evaluations to be completed. The subject will be permanently discontinued both from the study intervention and from the study at that time.
- If the subject withdraws consent for disclosure of future information, the sponsor may retain and continue to use any data collected before such a withdrawal of consent.
- Subjects who withdraw from the study may request destruction of any samples taken and not tested, and the investigator must document this in the site study records.

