- a Dosing must occur on Day 1, on the same day as randomization. The duration of subject participation in this trial may be variable. In Part 1, subjects may receive open-label treatment through Day 7 or resolution of ARDS (whichever occurs earlier). A DMC will review safety data from Part 1 and determine whether Part 2 can be initiated and whether Part 2 treatment can be extended beyond Day 7. Required criteria for initiation of Part 2 will include (1) no fatal/life-threatening SAEs thought possibly related to APL-9 by the DMC, and (2) no more than 1 subject requiring premature treatment discontinuation by the investigator due to AEs or abnormal laboratory tests. In Part 2, dosing may be extended only in subjects who still require respiratory support (oxygen supplementation or mechanical ventilation) at Day 7 with an improved PaO2/FiO2 ratio of at least 20 mm Hg from baseline if ABG test results are available for comparison. If ABG test results are not available, an improvement of FiO2 of at least 4% in nonventilated subjects (eg, those on nasal cannula) and 10% in mechanically ventilated subjects is needed. FiO2 should be weaned following the site's protocol to keep oxygen saturation at 89% or above. Treatment beyond Day 7 and through any DMC-approved extension will be at the discretion of the investigator. In Part 2, subjects will receive treatment up to and including the DMC-approved treatment duration, discontinuation of respiratory support (oxygen supplementation or mechanical ventilation), or hospital discharge (whichever occurs latest). Through Part 2, the DMC may review efficacy and safety data and recommend changes to the study conduct on an ongoing basis, but it will be required to review efficacy and safety data after the 10th and 30th subjects reach the DMC-approved treatment duration, discontinuation of respiratory support, or hospital discharge (whichever occurs latest). Enrollment will not be suspended during the DMC reviews. Subjects who reach the end of the approved treatment duration, discontinuation of respiratory support, or hospital discharge (whichever occurs latest) must be assessed as indicated in the EOT and discharge day column (for example, a subject who reaches the end of the approved treatment and achieves discontinuation of respiratory support on Day 6 should be evaluated with a radiograph or CT scan even though it is not indicated as a Day 6 assessment). All subjects will be followed up at the safety follow-up assessment 30 days after last study treatment (up to and including Study Day 51 with a +7-day window), either in person (for subjects still hospitalized) or by phone (for subjects who have been discharged).

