## 11. STUDY ASSESSMENTS AND PROCEDURES

- Day 1 is defined as the day upon which study treatment is first administered.
- The last predose assessments will be considered as baseline assessments.
- Study procedures and their timings are summarized in the SoA (Table 1). Protocol waivers or exemptions are not allowed.
- Significant safety concerns should be discussed with the sponsor immediately upon occurrence or awareness to determine whether the subject should continue or discontinue study participation.
- Adherence to the study design requirements, including those specified in the SoA (Table 1), is essential and required for study conduct.
- All screening evaluations must be completed and reviewed to confirm that potential subjects meet all eligibility criteria. The investigator will maintain a screening log to record details of all subjects screened and to confirm eligibility or record reasons for screening failure, as applicable.
- Procedures conducted as part of the subject's routine clinical management and obtained before signing of the informed consent form (ICF) may be utilized for screening or baseline purposes provided that the procedures met the protocol-specified criteria and were performed within the time frame defined in the SoA (Table 1).
- The study end-of-treatment assessments are to be conducted at the end of treatment or on the day of hospital discharge, whichever occurs later. The posttreatment follow-up assessment, conducted 30 days after the last dose of study drug (with a +7-day window), may be conducted either in the hospital or by telephone so that subjects do not have to be exposed to the hospital environment after hospital discharge.
- Discharged subjects will be provided with emergency study cards that include a list of symptoms associated with infections. The study card also guides subjects with instructions to contact their study physicians or seek emergency medical care in the event they experience any of the listed symptoms.

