6.2 Analysis of Secondary Efficacy Endpoints

6.2.1 Time-to-event endpoints

The following time-to-event endpoints are defined as:

- Hospital length of stay: initiation of study drug (Day 1, for Part 1) or randomization date (for Part 2) to hospital discharge. For subjects with death of any cause or withdrawal of study participation, hospital length of stay will be imputed with the longest hospital length of stay observed in the study.
- Overall survival: initiation of study drug (Day 1, for Part 1) or randomization date (for Part 2) to death of any cause; censored at the last day known to be alive.
- Total duration of mechanical ventilation defined as days on mechanical ventilation during the study participation, calculated as follows:
 - For subjects with death of any cause (or withdrawal of study participation), total duration of mechanical ventilation will be imputed with the longest duration observed in the study.
 - For any subject who is on mechanical ventilation at the initiation of study drug (Day 1, for Part 1) or at the randomization date (for Part 2), total duration of mechanical ventilation is calculated from Day 1 or randomization date.
 - For any subject who is not on mechanical ventilation at the initiation of study drug (Day 1, for Part 1) or at the randomization date (for Part 2), patient will be excluded.
- Total duration of oxygen therapy defined as days on mechanical ventilation or supplemental oxygen during the study participation, calculated as follows:

- For subjects with death of any cause (or withdrawal of study participation), total duration of oxygen therapy will be imputed with the longest duration observed in the study.
- For any subject who is on mechanical ventilation or supplemental oxygen at the initiation of study drug (Day 1, for Part 1) or at the randomization date (for Part 2), total duration of oxygen therapy is calculated from Day 1 or randomization date.
- For any subject who is not on mechanical ventilation or supplemental oxygen at the initiation of study drug (Day 1, for Part 1) or at the randomization date (for Part 2), patient will be excluded.

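### Protocol 10.2 lets the investigator take a subject off the whole study, overlaps 10.1 with no rule to choose between them, and conflicts with the general 30-day follow-up statements, so later SAEs and deaths could go unseen

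*Protocol*

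**What the plan says.** Protocol 10.2 covers two kinds of exit together: the subject's own request, and removal "at the discretion of the investigator for safety, behavioral, compliance, or administrative reasons". For both it asks for an end-of-treatment visit where that can be done. It then says "The subject will be permanently discontinued both from the study intervention and from the study at that time". The sentence just before points the other way: "See the SoA for data to be collected at the time of study discontinuation and follow-up and for any further evaluations to be completed".

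Protocol 10.1 deals with stopping study drug: "If study treatment is definitively discontinued, the subject will remain in the study to be evaluated for safety". It adds that a subject who stops treatment early or "is withdrawn from the study early because of a TEAE, whether serious or nonserious, will be followed up until the TEAE resolves", stabilizes, or is judged no longer clinically significant.

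Protocol Section 11 has significant safety concerns discussed with the sponsor at once "to determine whether the subject should continue or discontinue study participation".

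Other parts of the protocol describe follow-up in general terms. Footnote a of the Schedule of Assessments says "All subjects will be followed up at the safety follow-up assessment 30 days after last study treatment". Section 7.1 makes the 30-day assessment a requirement in Part 2. Section 11.2.5 collects AEs and SAEs through that assessment. None of the three makes an exception for early exit.

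In the SAP, Section 7.1 reports TEAEs and SAEs as numbers and percentages of subjects in the safety set, up to 30 (+7) days after the last dose. Section 6.2.1 has overall survival "censored at the last day known to be alive". The same section gives withdrawn subjects, like those who die, the longest observed value for hospital stay, ventilation duration and oxygen duration.

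**The concern.** One adverse reaction can be handled in two ways. If the investigator stops the drug, 10.1 keeps the subject in the study and the 30-day assessment follows. If the investigator removes the subject from the study, 10.2 reads as closing the subject out that day. Nothing says which route applies.

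Study exit for safety is an expected route. Section 11 frames a significant safety concern as a decision on participation. Section 11.2.5 records whether each AE led the subject to leave the study. SAP 7.1 plans a table of TEAEs leading to study discontinuation, separate from the one for treatment discontinuation.

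The primary endpoint is the cumulative incidence of treatment-emergent SAEs and TEAEs, and any-cause mortality is a secondary endpoint. Both run to the 30-day assessment. A subject removed for safety stays in the safety-set denominator, while later events may not be recorded, and is censored alive for survival. That loss is related to outcome, and in arms of about 30 one or two such subjects are visible in the result.

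**Working it through.** **Step 1. What is secured after an investigator-initiated exit.**

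| Information after exit | Text that keeps it | Text that ends it |
|---|---|---|
| The TEAE that caused the exit, including a fatal outcome | 10.1, with fatal as a recorded outcome in 11.2.4 | None that overrides 10.1 |
| New TEAEs and SAEs to 30 (+7) days after last dose | Footnote a, 7.1, 11.2.5, and 10.2's pointer to the schedule | 10.2: off study at that time |
| Death from another cause | The same, plus footnote i, which lists survival among the recorded items | 10.2, as above |
| Any later event after an exit for conduct, compliance or administrative reasons | The same general statements; the TEAE clause in 10.1 does not apply | 10.2, as above |

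Only the first row is settled. In the other three, a specific exit rule stands against general follow-up statements, and no text says which prevails.

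**Step 2. The plan's own figure.** Protocol 12.1 gives the chance of at least one SAE with about 30 subjects per arm. The formula is 1 − (1 − p)^30.

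- p = 1%: 26.0% (stated 26%)
- p = 4%: 70.6% (stated 71%)
- p = 7%: 88.7% (stated 89%)
- p = 10%: 95.8% (stated above 95%)

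The figures reproduce. If two of 30 subjects contributed nothing at all, p = 10% would give 1 − 0.90^28 = 94.8%, just below the stated 95%. That is a worst case, because events before exit are still counted.

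**Step 3. Size per subject.** The input is 30 subjects per arm (Protocol 12.1).

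- One unseen death, or one unseen SAE in a subject with no SAE already counted: 1/30 = 3.3 points.
- Two such subjects in one arm: 2/30 = 6.7 points.
- Any-TEAE percentage: usually 0 points. SAP 7.1 counts subjects, and one removed for safety will normally already have a counted TEAE.

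**Step 4. Range under assumed risks.** None of these risks is in the documents. Let w of 30 subjects exit early with later events unseen. Let event risk be 20% in retained subjects and q in those who exit.

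- True risk = [(30 − w) × 0.20 + w × q] / 30
- Crude percentage, denominator 30 = (30 − w) × 0.20 / 30
- Censored analysis = 20.0%, from retained subjects only

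| w | True risk, q = 20% to 80% | Crude | Censored |
|---|---|---|---|
| 1 | 20.0% to 22.0% | 19.3% | 20.0% |
| 2 | 20.0% to 24.0% | 18.7% | 20.0% |
| 3 | 20.0% to 26.0% | 18.0% | 20.0% |

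The crude SAE percentage is low even when exits are unrelated to risk. Censored survival is biased only when those who exit have a different risk from those who stay.

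**Step 5. Direction.** An unseen SAE or death makes the arm with the exit look safer. For hospital stay, ventilation and oxygen duration, the same exit receives the longest observed value and makes that arm look worse.

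**The case against.** The strongest reply is that follow-up is already required. Section 10.2 itself refers to the schedule for follow-up data, and footnote a, Section 7.1 and Section 11.2.5 carry no exception for early exit. Section 10.1 follows the triggering event to its outcome, so the death most relevant to a safety removal would be captured. Section 11 also brings the sponsor into significant safety concerns. All of this stands, and it limits the problem to the last three rows of the table in Step 1.

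A reader might infer more than the text supports in three ways:

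- **That 10.2 ends safety collection.** It does not clearly do so, because the follow-up statements remain in force beside it. The defect is that the two cannot both be applied.
- **That 10.2 contradicts 10.1.** Section 10.1 governs stopping treatment and 10.2 governs leaving the study, and 10.1 itself names both. They overlap for safety reasons without a deciding rule, which is a different fault.
- **That the bias consistently favors APL-9.** It could do so for SAE incidence and mortality if safety exits were more frequent on APL-9. The imputation in SAP 6.2.1 pushes three other endpoints the other way.

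The reply does not remove the practical risk. A site that reads the explicit statement that the subject is off the study at that time could reasonably close the subject out.

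**Conclusion.** The point holds as a conflict in the follow-up rules. Section 10.2 permits investigator-initiated exit from the whole study with no withdrawal of consent, overlaps 10.1 without a rule to choose, and conflicts with footnote a, Sections 7.1 and 11.2.5, and its own pointer to the schedule. What may be lost is new SAEs, deaths from other causes, and all later events after exits not caused by a TEAE.

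The size is about 3.3 points of SAE incidence or mortality in the affected arm for each such subject, with usually no change in the any-TEAE percentage. This assumes 30 subjects per arm, an event that is truly unseen, and, for SAE incidence, no SAE already counted in that subject. The documents give no expected rate of investigator-initiated withdrawal, so the total effect cannot be stated. This is a cheap improvement to the wording and does not call for a change of design.

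**What to change.** Reconcile Protocol 10.1, 10.2, Section 11 and footnote a of the Schedule of Assessments so that discontinuation initiated by the investigator does not end data collection.

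- In 10.2, state that every dosed subject has AE and SAE status, discharge date and vital status collected at the scheduled 30 (+7)-day safety follow-up, by phone, inpatient check or chart. The only exceptions would be withdrawal of consent to data collection, or loss to follow-up under 10.3.
- In Section 11, align the wording on study participation with this, so that a decision taken on a safety concern leaves follow-up in place.

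The cost is a few sentences of protocol text and a contact already scheduled for all other subjects. The downside is that sites must keep contact with a few subjects they would otherwise close out.
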